Brachial Artery Flow-Mediated Dilation (FMD). FMD will be measured to assess vascular endothelial function as a functional index of the impact of each beverage's ingestion on arterial blood flow. In brief, FMD is determined by a blinded, trained research assistant using an Acuson 13 MHz linear array transducer and a cardiac ultrasound system. Echocardiogram (ECG) is used to monitor heart rate throughout the procedure. Prior to testing, the participant is resting in the supine position for 10 min. Using ultrasound, the brachial artery will be located and the transducer will be secured in place to ensure consistent image acquisition. FMD measurements will be conducted by placing an inflatable cuff just below the antecubital fossa (crease of the elbow). The procedure is initiated by obtaining resting images (30 sec) of the brachial artery, followed by arterial occlusion (5 min) using the aforementioned inflatable cuff. The cuff is then rapidly deflated and post-occlusion ultrasound images are collected for 300 heart beats, which are analyzed using semi-automated software to calculate the ECG-gated measurement of dilation responses. Post-occlusion vessel diameters at 1 and 3 min, and peak diameter, will be used to calculate percent dilation relative to the pre-occlusion diameter. Post-occlusion peak blood flow velocity will also be collected simultaneously to normalize FMD responses to shear-stress (i.e. post-occlusion blood flow).

Carotid Intima Media Thickness (cIMT). cIMT will be measured at baseline of each trial to assess vascular endothelial function. While anticipated to be unchanged during the study, its assessment will allow for its consideration as a statistical co-variate in defining physiologic responses to test beverages. Images of the right- and left-sided far wall of the common carotid artery will be recorded for ~10 heartbeats and analyzed using edge-detection software to obtain mean, maximum, and minimum lumen diameter, and cIMT. Plaque

is defined by the presence of focal wall thickening that is $\geq 50\%$ greater than that of the surrounding vessel wall or ≥ 1.5 mm cIMT protrusion that is distinct from the adjacent boundary.

Sample Handling. Ultrasound images of the brachial and carotid arteries and blood flow data will be stored on the computer that is used to collect the data. Only a study code will be used to identify participants. At each time point, a blood sample (15 mL; 1 tablespoons x 7 time points = 105 mL or ~ 0.5 cups) will be collected into evacuated blood collection tubes. Throughout the span of the study which consists of the acute ingestion of 4 types of beverages for Objectives 1 and 2 and 1 screening day, we will be collecting a total of ~ 435 mL or ~ 2 cups of blood. For Objective 3, occurring in a separate cohort, consists of the acute ingestion of 3 types of beverages and 1 screening day, we will be collecting a total of ~ 330 mL or ~ 1.5 cups of blood.

During each trial, plasma will be obtained by centrifugation, and then transferred to cryogenic storage tubes. Tubes will be stored at -80°C until analysis can be completed. Analyses will include plasma glucose, insulin, triglyceride, total cholesterol, metabolites of NO (nitrite/nitrate), vasoactive markers (arginine, asymmetric dimethylarginine, tetrahydrobiopterin, dihydrobiopterin, endothelin-1, 11dehydro thromboxane B₂), antioxidants (vitamins E and C) and markers of oxidative stress (malondialdehyde and methylglyoxal). Remaining plasma sample aliquots not used for these analyses will be archived for 5 years at -80°C in the event we decide to measure additional inflammatory or antioxidant related markers. Appropriate notation has been made in the informed consent to alert participants that we will be archiving specimens and that they have the right to refuse our use of these specimens for future analyses. Lastly, approval from OSU IRB will be sought via a protocol amendment prior to the analysis of any additional biomarkers not specified herein.

Privacy/Confidentiality. For all data and records that are a part of this study, a number (i.e. code) will be assigned to each participant, and will only be available to research personnel. Any records containing the names of participants will be stored in a locked filing cabinet or on a password protected computer in the PI's laboratory or office. Research personnel under the supervision of the PI and the PI himself will be the only individuals that have access to this information. The names of participants will not be used for publication in any form. The records will be maintained until the data are published, up to a maximum of five years. All archived samples will be coded, but the key linking the code to each participant's identifiable information will have been destroyed. In addition, participants will be instructed that their participation in this study is voluntary and that they may withdraw at any time without prejudice. Data (food records and biochemical values) obtained from this study will be stored on a computer in the PI's laboratory. In addition, a back up of digital data will be stored on the PI's computer in his office. Both computers are password protected and both doors are locked when they are not in use.

Measurement / Instrumentation

For all *Objectives*, the below procedures will be utilized. All biomarkers and functional indices of vascular health will be assessed prior to (0 min) and at 30 min intervals for 3 h postprandially following ingestion of each test beverage unless otherwise noted. Other parameters will be measured during participant screening and/or at baseline (0 min) for each trial, as indicated.

Anthropometric Parameters and Blood Pressure. At screening and postprandially, participants will rest for 15 min prior to determining blood pressure. BMI will be calculated from height determined from a wall-mounted stadiometer and weight from a calibrated scale. Waist circumference will be assessed at the level of the umbilicus using a nonflexible measuring tape.

Serum Chemistries. Plasma triglyceride, total cholesterol, glucose, and insulin will be measured by clinical assay (Pointe Scientific) or ELISA (ALPCO) at screening and throughout the 3 h postprandial period following ingestion of each test beverage. HbA1c will be measured at screening and baseline of each trial using an Alere Anfinion analyzer. This procedure involves pricking the finger for a small drop of blood to

be measured by the analyzer. Insulin resistance at baseline and screening will be calculated as: [(fasting glucose (mmol/L) * fasting insulin (μ IU/mL)/22.5].⁹⁶

Vascular Function Studies. High-frequency ultrasound will be used to assess postprandial brachial artery FMD, as we described,^{11, 40} in response to each test beverage. In brief, the transducer is placed above the antecubital crease of the arm and anterior and posterior walls of the brachial artery are visualized. Anatomical markers will be noted to identically place the transducer during all visits. Baseline artery diameter will be recorded for 60 heartbeats. Then, a blood pressure cuff placed on the forearm immediately distal to the olecranon process will be rapidly inflated to occlude the artery (200 mmHg, 5 min). VEF will be measured following distal occlusion because this better reflects endothelial-dependent and NO \bullet -mediated vascular dilation compared to upper arm occlusion.⁹⁷ Upon cuff release, arterial diameter will be assessed for 300 heartbeats (~5 min). Brachial artery images will be obtained using a 13 MHz linear array transducer and Terason T3000 ultrasound system. Image analysis will be performed using edge-detection software (Vascular Research Tools). Peak post-occlusion diameter will be calculated by identifying peak dilation, and averaging vessel diameters \pm 5 frames surrounding the peak. FMD is calculated as a percentage of baseline diameter and normalized to shear stress. FMD will be performed by the same technician and image analysis will be assessed independently by two technicians in a blinded manner. Our studies show that FMD responses between technicians are not different ($P>0.05$; CV <8%).

Ultrasound studies will also be performed as we describe⁴⁰ to define CVD risk by assessing carotid intima media thickness (cIMT) using established criteria.⁹⁸ cIMT is anticipated to be unchanged during the study, but its baseline assessment will allow for its consideration as a statistical co-variate in defining physiologic responses to test beverages. Images of the right- and left-sided far wall of the common carotid artery will be recorded for ~10 heartbeats and analyzed using edge-detection software to obtain mean, maximum, and minimum lumen diameter, and cIMT. Plaque is defined by the presence of focal wall thickening that is \geq 50% greater than that of the surrounding vessel wall or \geq 1.5 mm cIMT protrusion that is distinct from the adjacent boundary.⁹⁸

Vasoactive Markers. Nitrite/nitrate, the stable end-metabolites of NO \bullet , will be measured to define NO \bullet status using a spectrophotometric kit (Cayman Chemical).¹¹ Indirect assessment of eNOS activity in humans is not practical because of its degree of invasiveness. Instead, it will be assessed indirectly by measuring ADMA/ARG by HPLC-FL as we describe¹¹ and the BH₄/BH₂ ratio from deproteinized plasma by HPLC with sequential ECD-FL detection^{99, 100} as described by our collaborating investigator, Dr. [name].¹⁰¹ We will also assess inhibitors of eNOS, i.e. plasma ET-1 and 11-dehydro-TXB₂ by ELISA (Cayman Chemical).

Antioxidants/Oxidative Stress. We show that PPH does not affect plasma antioxidants, but increases lipid peroxidation.⁹ However, antioxidant status regulates BH₄ recycling.^{100, 102} To rule out potential antioxidant-BH₄ interactions on eNOS activity, plasma vitamin E and C will be measured at baseline of each trial using our routine HPLC methods.^{9, 10} To define mitigating activities of dairy milk and its constituents on oxidative stress, MDA, a lipid peroxidation marker and MGO, a reactive glycolytic product that induces oxidative stress, will be measured as we described by HPLC-FL⁹ and HPLC-UV⁵⁹ throughout the 3-h postprandial period for each trial.

Internal Validity

For all data and records that are a part of this study, a number (i.e. code) will be assigned to each participant. Test confections will be assigned a code as well. This will minimize measurement bias when performing analysis on dietary records, and biochemical markers because all samples/records will be coded. The codes will only be broken once data analysis has been completed and verified by the PI.

Data Analysis

Baseline comparisons between trials will be performed a paired t-test (*Objectives 1-2*) or 1-way RM ANOVA (*Objective 3*) to ensure no changes in participant health status. Other analyses will be performed by

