Regulation of Postprandial Nitric Oxide Bioavailability and Vascular Function By Dairy Fat

Research Protocol

To ensure an effective review by the Institutional Review Board, a full description of the planned research must be submitted with the Application for Initial Review. A research protocol provides the reader with background information of the problem under study, including the study rationale, a detailed plan for conducting the research involving human research participants, and a discussion of the potential importance of the research.

I. Objectives

The *objective of this application* is to define mechanisms by which dairy milk, and its protein and lipid fractions, protect against postprandial vascular dysfunction by reducing oxidative stress responses that limit nitric oxide (NO[•]) bioavailability to the vascular endothelium. Our *central hypothesis* is that *dairy milk ingestion by prediabetic adults will protect against PPH-induced vascular dysfunction through oxidative stress-dependent mechanisms that increase NO[•] bioavailability, independent of changes in blood pressure*. To test this, we will complete the following objectives: 1) define NO[•]-mediated vasoprotection of non-fat milk on PPH-induced vascular dysfunction, 2) define the independent vasoprotective mechanisms of milk proteins on postprandial vascular function, and 3) define vasoprotection by dairy fat on PPH-induced vascular dysfunction. Upon completing these studies, we expect to provide the first direct evidence that dairy milk, mediated through its vasoactive protein and lipid fractions, protects against vascular dysfunction otherwise induced by PPH. Thus, these studies will extend epidemiological evidence supporting cardioprotective activities of dairy while also facilitating translational messages that encourage dairy consumption to mitigate metabolic insults leading to vascular dysfunction.milk.

II. Background and Rationale

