Milk Peptides Improve VEF. Dairy contains bioactive constituents that improve VEF.¹² Whey and casein represent ~20% and 80% of milk proteins,⁷⁰ and both have vasoactive properties, but whey has received more extensive study.⁷¹⁻⁷³ We showed that NOP-47, a whey-derived peptide, improves postprandial VEF.¹¹ In a placebo-controlled cross-over study in adults, whey peptide (5 g) ingestion increased FMD at 30-90 min compared to fasting levels. Improved VEF was accompanied by an attenuation in the decline of NO[•] metabolites, suggesting that NOP-47 improves VEF in a NO[•] dependent manner. In support, mesenteric arteries incubated with whey peptide have greater endothelium-dependent relaxation that is abolished by inhibiting NOS.⁷⁴ In contrast, little is known about the vasoactivities of casein. Supplementation of a casein-derived lactotripeptide compared to sodium caseinate improved FMD in normotensive postmenopausal women.⁸¹ Further complicating are the lack of studies directly comparing vasoactivities of whey protein and casein, a knowledge gap this application will address by defining the relative potencies of these major milk proteins on VEF.

In **conclusion**, evidence shows that: 1) PPH increases CVD risk, 2) lowering PPH and oxidative stress mitigates vascular dysfunction in a NO[•]-dependent manner, and 3) dairy attenuates oxidative stress and PPH, which likely protects against vascular dysfunction by improving NO[•] bioavailability. This provides a compelling basis to study vasoprotective activities of dairy milk. In addition, our team has the expertise needed to perform controlled interventions that assess VEF, oxidative stress, and NO[•] homeostasis, thereby positioning us ideally to undertake these innovative studies that will advance the understanding of bioactive components of dairy milk.

Anticipated Results, Significance, and Potential Benefit

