Most studies examining dairy-dependent vasoprotection have focused on its anti-hypertensive activities with limited regard for other mechanisms that could improve VEF. While important, and as we discuss,¹² blood pressure-lowering activities of dairy are unlikely to fully explain its role in reducing CVD risk. Thus, expected findings from the proposed randomized controlled, cross-over trials are anticipated to be paradigm-shifting by mechanistically linking improvements in VEF by dairy milk, and its protein and lipid fractions, to reductions in PPH-induced oxidative stress responses that otherwise limit NO[•] bioavailability and increase CVD risk. Findings of this application are also expected to provide the first evidence attributing the relative vasoprotective activities of whey protein, casein, and dairy fat on PPH-induced vascular dysfunction in association with improvements in oxidative stress and NO[•] homeostasis. These collective findings are also directly translatable into evidenced-based recommendations supporting forthcoming revisions to the US Dietary Guidelines regarding dairy consumption.

Pitfalls and Alternatives

Based on our preliminary studies, we do not anticipate any conceptual or technical difficulties in this application.

III. Procedures Study Design

This IRB protocol addresses three objectives by completing two separate randomized cross-over studies in two separate cohorts of participants. For clarity, *Study 1* is a 4-arm cross-over study that addresses the work under *Objectives 1 and 2* and will utilize one cohort of participants. *Study 2* is a separate 3-arm cross-over study that addresses the work under *Objective 3* and will utilize a different cohort of participants. Each study aims to enroll 24 participants for a total of 48 participants for all of the anticipated work.

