Studies under Objectives 1 and 2 will be accomplished through a common 4-arm crossover study. For **Objective 1**, which will examine the inhibition of non-fat milk on PPH-induced vascular dysfunction, prediabetic men and women ($n = 24$) in the fasted state will ingest 75 g glucose dissolved in water or nonfat milk (2 cups; 473 mL) on two occasions separated by ≥ 7 d. We will then assess FMD and collect blood samples prior to and at 30 min intervals for 3 h following test beverage ingestion to examine VEF and biomarkers regulating NO[•] bioavailability. In **Objective 2**, which will define independent contributions of dairy proteins in regulating VEF, participants will ingest glucose (75 g) with isonitrogenous quantities of whey protein isolate or sodium caseinate (16.5 g in 473 mL water) on two occasions separated by ≥ 7 d. Identical to Objective 1, FMD and blood samples will be obtained at 30 min intervals for 3 h. For **Objective 3**, which will define vasoprotective activities of dairy fat, a separate cohort of prediabetic men and women ($n = 24$) will complete a 3-arm cross-over study by ingesting glucose (75 g), or glucose with non-fat milk or whole milk (2 cups; 473 mL) on three occasions separated by ≥ 7 d. Identical to Objectives 1-2, FMD and blood samples will be obtained at 30 min intervals for 3 h.

Sampling Criteria and Methods

Enrollment Criteria. Prediabetic men and women are an ideal study population because of their underlying vascular dysfunction and exacerbated PPH.⁸² They will be required to meet these **inclusion criteria**: a) prediabetes (fasting glucose 100-125 mg/dL and hemoglobin A1c 5.7-6.4%⁸³), b) 18-50 y of age, c) non-dietary supplement user, c) no medications affecting vasodilation, inflammation, or energy metabolism, e) no CVD, and f) nonsmoker. To improve homogeneity, we will only enroll individuals having blood pressure $<140/90$ mmHg and total cholesterol <240 mg/dL. Those having any of these **exclusion criteria** will not be enrolled: a) unstable weight (± 2 kg), b) vegetarian or dairy allergy, c) alcohol intake >3 drinks/d or >10 drinks/wk, d) ≥ 7 h/wk of aerobic activity, or e) women who are pregnant, lactating, or have initiated or changed birth control in the past 3-mo. For all studies, the washout period will be 7 d for men and 1 mo for women because women require vascular testing at the same time during their menstrual cycle to account for known changes in vascular reactivity.⁸⁴

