
Power Calculation and Statistics. A power calculation was performed to determine the fewest participants needed to complete the two separate proposed cross-over studies (i.e. *Objectives 1-2* and *Objective 3*). We used FMD data from our studies^{9, 10} and predicted that non-fat milk will protect against PPH-mediated decreases in FMD. Assuming no gender differences, which is consistent with our earlier studies in this area,⁸ 11 prediabetic adults are needed to reject the null hypothesis with 80% power ($P<0.05$). Thus, 24 male and female prediabetics will be enrolled to improve statistical power to >90% while also accounting for study attrition that may occur due to women requiring a longer washout period between trials (1 mo vs. 7 d). Although participants will complete all arms of each cross-over study, statistical analysis will be handled discretely to examine differences between trials within each *Objective*. Baseline comparisons between trials will be performed a paired t-test (*Objectives 1-2*) or 1-way RM ANOVA (*Objective 3*) to ensure no changes in participant health status. Other analyses will be performed by 2-way RM ANOVA to define time and treatment effects, and their interaction. In the presence of any significant effects, Bonferroni's post-test will be used to examine pair-wise differences. To better define postprandial responses between treatments, area under the curve ($AUC_{0-3\text{ h}}$) will be calculated for each biomarker to enable more sensitive comparisons of postprandial responses between treatments and simplify analyses to a paired t-test (*Objectives 1-2*) or 1-way ANOVA (*Objective 3*) as we described.^{9, 10} Lastly, to define correlations between study variables, we will perform multiple linear regression, controlling for within-subject repeated measures.⁸⁵

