Justification of Test Meals. In *Objective 1*, beverages will consist of 75 g glucose in 473 mL water vs. 75 g glucose in 473 mL non-fat milk. This volume of milk was chosen to be consistent with our work⁸ and recommendations of the US Dietary Guidelines for Americans. The amount of glucose administered (75 g) is equivalent to that of a standard oral glucose challenge. We fully acknowledge that test beverages in *Objective 1* are not isocaloric. While this might be viewed as a limitation, this approach is being specifically undertaken to determine the vasoprotective effects of non-milk mediated through an attenuation of PPH-dependent vascular dysfunction rather than through the displacement of carbohydrate. In *Objective 2*, protein is being administered at 16.5 g to reflect total protein of non-fat milk, rather than their proportional contributions in milk, to pharmacologically define each protein in regulating VEF. In *Objective 3*, beverages will consist of glucose (75 g; positive control) vs. glucose (75 g) ingested with non-fat milk or whole milk. Despite associations between dietary fat and CVD risk, experimental evidence is lacking to support: 1) widespread restrictions of fat-containing dairy foods, and 2) that dairy fat, which is predominately saturated fat, is causatively responsible for increasing CVD risk. This approach will enable an interpretation of the contribution of dairy fat in protecting against PPH-induced VED while providing findings to fill this research knowledge gap.

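### Study 1 gives milk, whey and caseinate to the same people but plans no comparison of milk with either protein, so no planned analysis supports the expected conclusion that milk acts through its protein

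*Combined protocol and SAP*

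**What the plan says.** Under Study Design (section III), Study 1 "is a 4-arm cross-over study that addresses the work under" Objectives 1 and 2, in one cohort of 24. Test Trials confirms that each participant takes all four drinks in random order.

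- **Objective 1** (Justification of Test Meals): "beverages will consist of 75 g glucose in 473 mL water vs. 75 g glucose in 473 mL non-fat milk".
- **Objective 2** (Study Design): 75 g glucose with "isonitrogenous quantities of whey protein isolate or sodium caseinate (16.5 g in 473 mL water) on two occasions".

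Power Calculation and Statistics sets the scope of testing: "Although participants will complete all arms of each cross-over study, statistical analysis will be handled discretely to examine differences between trials within each" Objective. Both that section and Data Analysis name a paired t-test for the AUC comparisons in Objectives 1-2, and an ANOVA for the three-arm Objective 3.

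Section I (Objectives) expects to show directly that "dairy milk, mediated through its vasoactive protein and lipid fractions, protects against vascular dysfunction otherwise induced by PPH". Anticipated Results expects first evidence "attributing the relative vasoprotective activities of whey protein, casein, and dairy fat on PPH-induced vascular dysfunction".

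On amounts, Justification of Test Meals states that "protein is being administered at 16.5 g to reflect total protein of non-fat milk, rather than their proportional contributions in milk". The Background gives the split: "Whey and casein represent ~20% and 80% of milk proteins".

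**The concern.** To say that milk protects through its protein, one must know at least whether protein alone protects, and how its effect compares with that of milk. Both questions need contrasts that cross the boundary between Objectives 1 and 2, and the plan rules those out.

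As written, Study 1 can report that milk differs from glucose and that whey differs, or does not differ, from caseinate. Neither result shows that a protein protects, or that protein reproduces the milk effect. The link would then rest on an informal reading of two separate P values, or on contrasts added after the results are known.

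The lipid part of the same sentence is better served. Objective 3 puts glucose, non-fat milk and whole milk in one analysis.

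**Working it through.** **1. Contrasts planned and omitted.** The four drinks are G (glucose), M (with milk), W (with whey) and C (with caseinate). They give 4 × 3 / 2 = 6 pairwise contrasts.

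| Contrast | Planned? |
|---|---|
| M − G | Yes, Objective 1 |
| W − C | Yes, Objective 2 |
| M − W | No |
| M − C | No |
| W − G | No |
| C − G | No |

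The paired t-test confirms two arms per Objective. The two-way RM ANOVA and its Bonferroni post-tests fall under the same restriction. The closing regression concerns correlations between variables and does not compare drinks.

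**2. The plan's own power figures.** The plan states 11 participants for 80% power at P<0.05, and more than 90% power with 24. It gives no FMD difference or SD, so 11 cannot be derived independently. Solving the paired t-test (noncentral t) backwards for 80% power at n = 11 gives a standardized paired difference dz of 0.94 two-sided, or 0.81 one-sided (sidedness is not stated). At n = 24 these give 99.3% and 98.6% power, which agrees with the plan's claim.

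**3. Precision of the omitted pairwise contrasts.** The unadjusted 95% half-width, in SD of a paired difference, is t(0.975, n−1)/√n. The attrition rate is not given, so n = 20 and 17 are assumptions.

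- n = 24: 2.069/√24 = 0.42
- n = 20: 2.093/√20 = 0.47
- n = 17: 2.120/√17 = 0.51

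**4. Power with a multiplicity adjustment.** With four added contrasts, Bonferroni gives alpha = 0.05/4 = 0.0125. By the same noncentral t calculation (two-sided), the dz detectable with 80% power is 0.73 at n = 24, 0.82 at n = 20 and 0.90 at n = 17. Without adjustment it is 0.60, 0.66 and 0.72.

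Power at n = 24 and alpha = 0.0125, by size of the true difference relative to dz = 0.94, is:

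- equal to it: 96%
- three quarters: 76%
- half: 36%
- a quarter: 8%

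A modest milk-protein difference would often be missed, so a non-significant result cannot be read as equivalence.

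**5. Amounts relative to milk.** Inputs are 16.5 g of each protein and the approximate 20%/80% split.

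- Whey in the milk drink: 0.2 × 16.5 = 3.3 g, and 16.5/3.3 = 5.0 times.
- Casein: 0.8 × 16.5 = 13.2 g, and 16.5/13.2 = 1.25 times.

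**6. A weighted contrast, for exploration only.** Take M − (0.2 W + 0.8 C). The weights on the protein drinks sum to 1, so glucose alone cancels. With equal variances and correlations, the variance is proportional to 1 + 0.04 + 0.64 = 1.68, against 2.00 for a pairwise contrast. The SE ratio is √(1.68/2.00) = 0.917. Multiplying the half-widths in step 3 by 0.917 gives 0.39, 0.43 and 0.47 for 24, 20 and 17 completers.

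**The case against.** The strongest reply is that the plan does not set out to partition the milk effect. Its central hypothesis concerns milk acting through oxidative stress and nitric oxide. The Background names the gap for Objective 2 as the absence of head-to-head studies of whey and casein, and equal amounts of each address that. Anticipated Results speaks of relative activities, not shares of the milk effect. This stands: the overreach on milk acting through protein lies mainly in one sentence of section I. That sentence is still a stated expected result, described as direct evidence. Objective 2 also speaks of vasoprotection by the proteins, which whey against caseinate alone cannot show.

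Three stronger readings are tempting, and the documents do not support them.

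- **That the whey amount is an error, or inflates whey's share of the milk effect five-fold.** Justification of Test Meals discloses the amount and gives a pharmacological reason. A five-fold overstatement would need effect proportional to amount, and a whey-against-glucose estimate that the plan never produces. The amounts only limit what the whey arm says about whey as it occurs in milk.
- **That attributing the milk effect to protein is the stated reason for using one cohort.** Study Design says only that the two objectives share a common cross-over study.
- **That the weighted contrast would settle attribution.** Because glucose cancels, a value near zero also fits no effect of milk or of protein. It further assumes proportional and additive effects, which one amount of each protein cannot test.

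**Conclusion.** The gap is real. Four of the six pairwise contrasts in Study 1 are unplanned, including both of milk with a protein and both of a protein with glucose. The expected conclusion that milk acts through its protein fraction therefore has no planned analysis behind it. This follows from the text and needs no assumption.

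The precision figures do rest on assumptions: a two-sided paired t-test, an assumed 17 to 24 completers, and AUC as the scale, although the plan does not say that its sample size was calculated on AUC. On that basis the added contrasts would be informative for differences near the size of the implied milk effect and weak for differences of half that size or less. Even with them, the study would compare drinks and would not be a formal mediation analysis.

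This is a cheap improvement that should be made before the codes are broken. It does not undermine the planned test of milk against glucose.

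**What to change.** In Power Calculation and Statistics and in Data Analysis:

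1. Analyse all four Study 1 drinks in one within-person model of FMD AUC over 0-3 h. Keep milk minus glucose and whey minus caseinate as planned.
2. Prespecify as secondary, with 95% confidence intervals and a stated multiplicity adjustment, milk minus whey and milk minus caseinate. These match total protein and need no proportionality assumption. Read them together with whey minus glucose and caseinate minus glucose.
3. State that a non-significant milk-protein difference will not be read as equivalence.
4. If the weighted contrast is shown, label it exploratory and state its proportionality and additivity assumptions.

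In section I, limit the wording on milk acting through its protein to what these contrasts support. When reporting the whey arm, carry forward the existing disclosure that the amounts do not reflect proportions in milk. No change to any drink is proposed.

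The cost is four added contrasts on data already to be collected, and a stricter threshold for them. With Bonferroni over four at 24 completers, the difference detectable with 80% power rises from 0.60 to 0.73 SD of a paired difference. No visit, sample or participant is added.
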